Official Title: Using Real-Time Data Capture to Examine Affective Mechanisms as Mediators of Physical Activity Adherence in Interventions: Formative Study

NCT #: NCT06125964

Document: Study Protocol

Date: 04.02.25

Study Procedures

1. Background/Rationale

Cancer is responsible for 600,000 deaths per year in the United States. Of these cases, 15% are potentially avoidable through adequate physical activity and weight maintenance.¹ Despite public health guidelines outlining the frequency, duration, and intensity of exercise needed for these protective benefits, however, large-scale accelerometry research reveals that more than 95% of American adults remain physically inactive.² To increase the probability of physical activity engagement, researchers have previously manipulated individual cognitions,^{3,4} targeting constructs such as self-efficacy, outcome expectancies, and intentions.⁵⁻¹⁰ These interventions have had limited success. Research is desperately needed to elucidate novel mechanisms—beyond cognitive processes—that might change physical activity behaviors.

The type, context, and affective responses surrounding physical activity engagement represent valuable mechanisms that might be contributing to the exercise intention-behavior gap.¹¹ Recent evidence suggests that affect, independently of cognitive processes, is a powerful predictor of physical activity engagement and enjoyment.¹²⁻¹⁶ Exercise itself elicits robust changes to emotional states, triggering affectively-charged motivations that—per incentive salience theory—lead to pursuit or avoidance of future associated behaviors.¹⁷ While many individuals react positively to light intensity exercise and negatively to vigorous intensity exercise,¹⁸ great inter-individual variability exists in the affective response to moderate intensity physical activity.¹⁹⁻²² For example, individuals with overweight/obesity or who are typically inactive are more likely to experience unpleasant feelings when exercising.²³ This can harm their intentions to maintain healthy levels of activity over time.²⁴ Research shows that part of the heterogeneity in affective response is due to the activity type (e.g., dance, yoga, brisk walking)^{25,26} and context (e.g., being with others or outdoors).²⁷⁻³⁴ Interventions that leverage activity types and contexts to strategically increase favorable affective responses might therefore improve physical activity maintenance in groups vulnerable to avoidable cancers.

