Orientation. Once study materials are received, the participant attends a remote orientation session where they will be introduced to the study and watch a summary presentation with instructions on how to participate. During this session, participants are led through setting up their smartphone and Fitbit Versa smartwatch to our study platform through Fitabase, to allow for tracking of physical activity and delivery of EMA ("check-ins"); study staff then teach them how to complete smartphone based morning and evening goal sessions and how to respond to EMA ("check-ins") on their Fitbit smartwatch.

Random Assignment. Random assignment will be stratified by sex at birth and assigned using the randomization allocation table via REDCap. Participants will be assigned to one of eight groups (n=45 each), based on order and intervention components: Intensity > Affect (No Enhancements), Intensity > Affect (Tailored Recommendations), Intensity > Affect (Savoring), Intensity > Affect (Tailored Recommendations & Savoring), Affect (No Enhancements) > Intensity, Affect (Tailored Recommendations) > Intensity, Affect (Savoring) > Intensity, Affect (Tailored Recommendations & Savoring) > Intensity.

[figure not shown]
Run-in Period. The Comparison Study will begin with a week-long Fitbit smartwatch assessment-only run-in period to introduce participants to wearing and charging the Fitbit smartwatch and collect baseline physical activity data.

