The 19-week Comparison study (N=360) will then use a Multiphase Optimization Strategy (MOST) design to determine the effects of each intervention component.^{37,38} Specifically, we will compare affect- and intensity-based goals within-persons and affect-based goal condition enhancements between-persons (Figure 1). Participants are randomly assigned to treatment groups. The study protocol begins with a run-in period (described above), followed by either affect- or intensity-based goals for the first 8-weeks, a two week washout period, and a cross-over to receive the alternate condition for the remaining 8-weeks. During the affect-based goal condition, participants also randomly receive one of four possible combinations of TYPE/CONTEXT and SAVOR enhancements: [1] affect-based goal setting alone; [2] affect-based goals + TYPE/CONTEXT; [3] affect-based goals + SAVOR, [4] affect-based goal setting + TYPE/CONTEXT + SAVOR.

Figure 1. Comparison Study Design

Note. ^a Brief savoring experiences; ^b Tailored recommendations for activity types and contexts to satisfy important psychological needs.

Intervention

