AIM 1: Determine whether affective mechanisms can be experimentally manipulated. In the Formative study, descriptive statistics (means, frequencies) will assess acceptability and feasibility of content, delivery methods, device usage, engagement, and raw values for change in affective mechanisms. The Comparison study will use an “intent to treat” approach to test the (1) within-subject effects of affect- vs. intensity-based goals (H1), (2) between-subject effects of affect-based goals with vs. without TYPE/CONTEXT (H2), and (3) between-subject effects of affect-based goals with vs. without SAVOR (H3) on the primary outcome (affective responses and affectively-charged motivations) and secondary outcome (physical activity). We will use random-effect regression models (level 1-days, level 2-subjects), which adjust for clustering within subjects and incorporate random effects.¹⁰⁷ Each treatment effect and each outcome will be tested in separate models. We will examine cross-level interactions between affect-based goals with vs. without savoring (level 2) and affective responses (level 1) to test H3.

AIM 2: Determine whether affective mechanisms mediate effects of interventions on physical activity (Comparison Study). Multilevel mediation will be tested using a 1-1-1 strategy that fits a set of simultaneous equations using path analysis in R.¹⁰⁸ Analyses will test the effects of intervention engagement on same-day/same-week affectively-charged motivations and affective response; the effects of affectively-charged motivations on same-day/same-week physical activity and the effects of affective responses on next-day/next-week physical activity; the indirect effects of intervention engagement on same- and next-day/same- and next-week physical activity via affective mechanisms (H4); and the total effects (mediated plus unmediated) of intervention engagement on physical activity.

AIM 3: Explore cross-person and cross-situation moderating effects (Comparison study). We will add interaction terms for time-varying and time-invariant effect moderators (H5).¹⁰⁹

Dissemination of Findings

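### H1 is a pooled cross-over contrast that relies on a two-week washout, with no period, order or carryover analysis; any differential carryover biases it by half the difference

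*Combined protocol and SAP*

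**What the plan says.** The Intervention Period section describes a one-week run-in, 8 weeks on one goal type, then "a two week washout period, and a cross-over to receive the alternate condition" for the last 8 weeks: 1 + 8 + 2 + 8 = 19 weeks. Under Random Assignment, "Participants will be assigned to one of eight groups (n=45 each), based on order and intervention components". Four groups start with intensity and four with affect, so 180 of the 360 participants follow each order.

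Under Data Analysis, Aim 1, the first comparison is the "within-subject effects of affect- vs. intensity-based goals (H1"), on affective responses and affectively charged motivations (primary) and physical activity (secondary). The method is stated as: "We will use random-effect regression models (level 1-days, level 2-subjects), which adjust for clustering within subjects and incorporate random effects". It adds: "Each treatment effect and each outcome will be tested in separate models".

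The confounders listed for the Comparison Study are age, sex, income, race/ethnicity, BMI and fitness. Other variables may enter through a p < .10 screen. Period, order, carryover and a first-period analysis are not mentioned. No reason is given for the two-week washout. The Compensation section shows that the Fitbit is worn during it, but no analysis of those data is planned.

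**The concern.** Including a washout acknowledges that the first phase may affect the second, but nothing in the analysis would show whether two weeks were enough.

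Persistence is plausible on the plan's own reasoning. Section 1 describes exercise as "triggering affectively-charged motivations that" draw people toward related behaviour later or turn them away from it, and it hopes that affect-based approaches will help people stay active. The TYPE/CONTEXT enhancement tells participants which activities and settings suit them, and that knowledge cannot be withdrawn. The intensity goal sets a minimum heart rate and, as described, does not restrict activity type or setting. An affect-first participant could therefore go on using what was learned. The intensity phase, with heart-rate goals rising over 8 weeks, could leave a benefit of its own.

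At stake is the H1 estimate and how it is read. A small pooled effect could mean that affect-based goals add little, or that their benefit spilled into the comparison phase. The planned model cannot tell these apart.

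**Working it through.** **Inputs from the Data Analysis section.** Effect on affective response f² = 0.04, equated with 0.3 points on a 5-point scale; N = 200 (100 per condition) after about 30% attrition; power 0.80 (printed as β); α = 0.05. Two-sided testing is assumed because the plan does not say.

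**Reproducing the plan's figure.** For two equal groups d = 2√f² = 2 × 0.2 = 0.40. Two-sided, this needs 99 per group, or 198, against the stated 200. Power at N = 200 is 0.804 by noncentral F. The implied SD is 0.3 / 0.40 = 0.75 (derived, not stated). The plan gives this figure for H2 and H3. For H1 it gives only a count of person-days, 200 × 4 × 4 × 7 = 22,400, with no allowance for carryover.

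**Bias of the pooled contrast.** Let τ be the true affect-minus-intensity effect, π the shift from period 1 to period 2, and λA and λI what the affect and intensity phases leave behind in period 2.

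- Affect-first, period 1 minus period 2: τ − π − λA.
- Intensity-first, period 2 minus period 1: τ + π + λI.
- Average of the two: τ − (λA − λI)/2.
- Period 1 only, affect-first minus intensity-first: τ.

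The period shift cancels from the average when the orders are equal in size. The carryover difference does not.

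With τ = 0.30 (the persistence shares are assumptions):

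| Carryover, as a share of 0.30 | Pooled H1 estimate |
|---|---|
| none | 0.300 |
| affect 25%, intensity 0 | 0.30 × (1 − 0.125) = 0.2625 |
| affect 50%, intensity 0 | 0.30 × (1 − 0.25) = 0.225 |
| affect 75%, intensity 0 | 0.30 × (1 − 0.375) = 0.1875 |
| affect 50%, intensity 50% | 0.300 |
| affect 0, intensity 50% | 0.30 × (1 + 0.25) = 0.375 |

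If only the savoring groups carried over (2 of the 4 affect-first groups, 90 of 180), the attenuation is halved: 0.281 at 25% and 0.2625 at 50%.

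**Effect on H1 power.** At N = 200, with an assumed correlation of 0.5 between phase means, power is above 0.99 without carryover, 0.989 at 50% and 0.807 at 100%. For correlations of 0.3 to 0.7 the 100% case runs from 0.67 to 0.96.

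**Unequal dropout.** Assume τ = 0.30, π = −0.2, and dropout of 20% in affect-first and 40% in intensity-first. The order-specific contrasts are 0.5 and 0.1, and the completers number 144 and 108. Completers alone give (144 × 0.5 + 108 × 0.1)/252 = 0.33. A random-intercept model that also uses the dropouts' first-period data gives 0.32. Reversing the dropout rates gives 0.28 in that model. A period term restores 0.30 in both cases.

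**The first-period comparison.** Power at f² = 0.04 is 0.804 at N = 200, and 0.885 if 360 × 0.70 = 252 complete. The standard error at N = 200 is 0.75 × √(2/100) = 0.106, against 0.75 × √(2 × 0.5)/√200 = 0.053 for the within-person contrast at correlation 0.5.

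**Why a carryover test is not enough.** A test on participants' two-period totals, at N = 200 and correlation 0.5, has power of only 0.07, 0.13 and 0.37 when 25%, 50% and 100% of the effect carries over.

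**The case against.** The strongest reply is that carryover is conjecture. A reader might infer that the affect condition teaches lasting preferences and savoring skills, so that H1 is necessarily pulled toward zero. The documents do not support that. SAVOR is described as enhancing and prolonging positive experience of activity, not as acting after the phase ends, and it reaches only half of the affect-first participants. The theory in Section 1 concerns exercise in general and speaks of avoidance as well as pursuit. The longest lag in the planned analyses is next-week, shorter than the washout. Goal setting, action planning, coping planning and self-monitoring occur in both conditions, so their carryover should largely cancel. The direction of any net bias is therefore open.

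Three further points stand. Balanced random order protects against a common time trend. Under moderate attenuation H1 would probably still be significant, and attenuation cannot create a false positive. Missing-data sensitivity analyses are already planned, though not by order.

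None of this fills the gap. The listed confounders omit period and order, and an order main effect admitted by the p < .10 screen would not correct carryover. Not knowing the sign is itself a reason to include a check.

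**Conclusion.** The point holds as a gap in the H1 analysis, not as a demonstrated bias. The pooled estimate departs from the truth by half the carryover difference. If intensity leaves nothing, 25% to 75% persistence of the affect effect costs 12.5% to 37.5% of it (0.30 becomes 0.26 to 0.19). Equal carryover costs nothing, and greater intensity carryover inflates the estimate. The persistence shares are assumptions, because the documents give no figure. The bias formula does not depend on the derived SD of 0.75 or the assumed correlation; the power figures for H1 and the carryover test do.

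The period issue is secondary: it matters only if dropout differs by order, and it moved 0.30 by about 0.02 in the illustration. The main harm is to the size and interpretation of H1 rather than to its chance of significance.

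**What to change.** In the Aim 1 analysis for H1:

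1. Add a fixed period term to each model. This handles a time trend under unequal dropout; it does not remove carryover. A sequence main effect would not remove it either.
2. Report the within-person H1 estimate by order, as description. The gap between the two orders is 2π + λA + λI, so it mixes time trend with carryover and does not by itself diagnose carryover.
3. Pre-specify a first-period comparison of affect-first with intensity-first participants as a sensitivity analysis, shown beside the within-person result, which stays primary. Adjust it for run-in baseline only for physical activity, since no run-in measure of affective response or motivation is described.
4. State that no data-driven rule will choose between the two results. With no treatment effect and no carryover, switching to the first-period result when the estimates differ by more than 0.10 or 0.15 points, or when a 10%-level carryover test is significant, raises simulated type I error from 5% to about 7–9% (SD 0.75, 100 or 126 per order, correlations 0.3 to 0.7).

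The Fitbit data from the washout could also be summarised by order to describe whether activity differences persist.

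The cost is some added wording and one more model per outcome. The first-period estimate is less precise, with about twice the standard error at correlation 0.5. The design and the washout are unchanged.

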This study will add affect-based physical activity goals to an existing mHealth intervention called MyDayPlan, which delivers morning and evening goal sessions. Every Sunday, participants receive a text message with a link to a brief REDCap questionnaire where they are asked about their tentative sleep and physical activity schedule for that upcoming week. On days participants have planned to do physical activity (according to the Sunday scheduling survey), they will engage in two goal sessions: one in the morning and one in the evening. Participants are alerted to complete a session with a text message that has a link to a REDCap form. Morning goal sessions provide an activity goal for the day (“goal module”); ask the participant to create a concrete plan for achieving this goal (“action plan module”); and prompt the participant to anticipate barriers and brainstorm solutions to accomplish the goal (“coping plan module”). Evening goal sessions have participants reflect on whether they were able to meet this goal (“self-monitoring module”). The focus of the goal module differs according to the participant’s assigned condition. For each condition, the Fitbit Versa smartwatch will feature a custom watch face with a clock (current local time), the date, current device battery levels, and a physical activity button. The physical activity button can be pressed whenever a subject wants to engage in physical activity, and provides real-time feedback on activity duration. If the subject’s moving average HR is too low following the physical activity button press, the Fitbit smartwatch will ask “Still exercising?” twice (options No; Yes) before auto-concluding the session. [Note: for the Comparison Study, the wording of this question will be “Still being physically active?”]. Participants will also have the option to view short explanatory videos throughout their participation that summarize aspects of what is expected of them in the study.

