slightly varied wording to promote a sense of novelty. Examples of the three prompts are: “(1) Think about the most positive part of your physical activity session today. What about this part made it positive to you? (2) Next, think about the positive feelings you experienced during this session. Please describe them. (3) Take a moment to appreciate your physical activity session today. What about it are you grateful for?”. Savoring prompts will rotate daily and have a day lag built in every week (i.e., Week 1 Monday Savoring Prompts are Week 2 Tuesday Savoring Prompts).

[figure not shown]
Instrumentation

Study variables will be collected with online questionnaires via REDCap surveys, smartwatch-based EMA (“check-ins”), smartwatch-based accelerometry, and an exit interview (Formative Study only).

Fitbit Versa smartwatch accelerometer: Participants will be loaned a Fitbit Versa smartwatch to be worn on the wrist for the duration of the study period, except while bathing. An internal accelerometer continuously measures physical activity intensity (sedentary, light, moderate, vigorous) and step count at the minute-level. **Heart rate (covariate)** is also recorded continuously and is used to determine smartwatch wear, as well as to calculate average heart rate during activity sessions >10 min. Only days with sufficient wear time (defined as ≥ 10 hours of valid data, where no more than 20 minutes per hour has a consecutive step count of zero) are used for analysis. **Daily steps and minutes of light, moderate, and vigorous physical activity (outcome)** are then calculated from minute-level data. Fitbit does not provide access to the raw acceleration data. However, activity intensities, steps, and heart rate measured by Fitbit devices have been shown to be reliable and valid as compared to other activity monitors including Actigraph.⁴²⁻⁴⁵

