EMA via Fitabase Engage: Real-time prompted EMA (“check-ins”) will be administered on the smartwatch using Fitabase Engage. If no interaction with the watch face is made, one reminder signal may be emitted before the prompt becomes inaccessible. EMA (“check-ins”) take approximately 30 seconds to complete. If a prompt occurs during an incompatible activity (e.g., driving), participants will be instructed to ignore it. To minimize participant burden, all questions are answered by tapping the smartwatch interface.^{46,47} **Three types of EMA (“check-ins”)**—random, event-contingent, and evening—will be sent to participants. Random and event-contingent are used for the Formative Study, while the Comparison Study will use event-contingent and evening. **Random EMA** (“check-ins”) will be randomly scheduled to be sent during normal waking hours, with a single prompt sent during each of four evenly spaced time windows: 0-4, 4-8, 8-12-, and 12-16-hours post-waking. Participants are asked to report their incidental affect via seven bipolar Likert Scale items. Five items (Energetic-Fatigued, Happy-Discouraged, Relaxed-Tense, Excited-Bored, Satisfied-Frustrated) are drawn from Russell’s Circumplex Model of Affect;⁴⁸ one (Good-Bad) represents core affective valence;⁴⁹ and one (Proud-Embarrassed) represents self-conscious emotion.⁵⁰ One of these seven items is repeated as a validity check (i.e., for a total of eight items). **Event-contingent EMA** (“check-ins”) are triggered when Fitbit sensors detect physical activity via moving average heart rate max. At least a 10-minute buffer (Formative Study) or 30-minute buffer (Comparison Study) separates the first and second event-contingent EMA during a single exercise bout, such that the moving average heart rate is “reset” following completion of the first prompt and the earliest possible second prompt is sent at least 10-minutes later (Formative Study) or 30-minutes later (Comparison Study) assuming the aforementioned threshold is met. A maximum of two event-contingent EMA will be sent within any given 60 min period. Participants are asked to safely pause their activity to answer questions about their **affective response (mediator)**^{49,51,52} with the same eight (i.e., 7 unique + 1 repeated) items as the random EMA above. Event-contingent EMA also include end a Rating of Perceived Exertion (RPE) item and end by asking whether the current physical activity is the participant’s planned session.⁵³ Finally, evening EMA (“check-ins”) are sent to participants at 8 pm local time every day and ask participants to report their feelings from that day using the same eight affective response items as the random and event-contingent EMA (only modified to ask about their overall affect from that day, rather than their current affect). A depiction of the daily intervention strategies and measures is shown in Figure 2.

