For the Comparison Study, participants will receive four payments of up to \$100 each (paid every 4 weeks): \$50 for wearing the Fitbit Versa smartwatch all day and night (≥ 23 h/day) and \$50 for answering all smartwatch EMA (“check-ins”; except for those that occur while driving, sleeping, or another activity that precludes responding). A \$50 payment will also be given during the 2-week “washout” break for wearing the Fitbit Versa smartwatch all day and night (≥ 23 h/day), and another \$50 payment will be given for completing the Baseline (\$20), Mid-Study (\$15), and Post-Study Questionnaire (\$15) s. The total possible compensation for the 19-week Comparison Study is \$500, and participants also keep the Fitbit Versa smartwatch upon completion. For the 120 participants in the Comparison Study sub-sample (recruited starting March 2025), the compensation structure will be the same, except they will instead receive four payments of up to \$120 each (paid every 4 weeks): \$60 for wearing the Fitbit Versa smartwatch all day and night (≥ 23 h/day) and \$60 for answering all smartwatch EMA (“check-ins”; except for those that occur while driving, sleeping, or another activity that precludes responding), and \$20 for completing an exit interview, for a total of \$600.

Participant Privacy & Data Management

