Exploratory analysis will examine the distributions, identify needed data transformations, investigate multicollinearity, and identify extreme observations. Data will be analyzed with SAS and R. Missing data analyses will involve considerations of imputation methods,^{93,94} attrition propensity scores⁹⁵ based on the compliance/dropout for each participant,⁹⁶ and sensitivity analyses. We will consider age, sex, income, Version 04.02.25

race/ethnicity, BMI, and fitness as confounders. Other variables associated with outcomes ($p < .10$) will be included as covariates. Exploratory tests of moderation will also be conducted, as there may be sex and age differences in physical activity^{97,98} and affective mechanisms.^{99–101} Power estimates were evaluated using Monte Carlo simulations in Mplus.^{102–105} The estimated effect size of affect-based physical activity interventions range from a small effect on the primary outcome (affective response) ($f^2 = 0.04$, representing a 0.3 point increase on a 5-point affect scale)⁵⁴ to a medium effect on the secondary outcome (physical activity) ($f^2 = 0.17$, representing a 30/min week increase in MVPA).¹⁰⁶ A sample of $N=200$ participants (100 per condition) (after ~30% attrition) is needed to detect small between-subject effects on change in the outcomes (H2 and H3) with $\beta = .80$ and $\alpha = .05$. To detect within-subject effects (H1 and H4), our level-1 sample sizes will be much larger (e.g., $200 \times 4 \times 4 \times 7$ level-1 N for daily data). Thus, we should have sufficient power to detect very small effects for the remaining associations. H5 is exploratory and not statistically powered.

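### The valid-day rule judges an hour by zero-step runs although heart rate is named as the wear signal, so a fully worn but sedentary day can be dropped from the physical activity analysis.

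*Combined protocol and SAP*

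**What the plan says.** Three adjacent sentences matter (5. Methods, Instrumentation, Fitbit Versa smartwatch accelerometer).

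- Heart rate "is also recorded continuously and is used to determine smartwatch wear".
- A day needs at least 10 hours of valid data. An hour is judged by its steps: "where no more than 20 minutes per hour has a consecutive step count of zero) are used for analysis".
- The quantities then derived are "Daily steps and minutes of light, moderate, and vigorous physical activity (outcome").

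Nothing says how the heart-rate statement and the step rule combine, or what happens to an hour with heart rate but few steps.

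Under Data Analysis, Comparison Study, AIM 1 makes physical activity the secondary outcome for H1-H3, with days as level 1 of the models. AIM 2 makes it the endpoint of H4, including a path from affective response to next-day activity. The missing-data text there proposes considering imputation, propensity scores "based on the compliance/dropout for each participant", and sensitivity analyses. It does not mention worn days lost to the step rule.

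**The concern.** A wear rule should separate days on which the watch could record activity from days on which it could not. A zero-step run does not do that, because an hour of sitting with the watch on looks the same as an hour with the watch off. Heart rate can tell the two apart, and the protocol says it is recorded for that purpose.

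The sample is recruited for doing less than 60 minutes of structured activity a week (3. Participants), so long sitting runs on worn days are plausible. If such days are filtered out, the analysed days are selected on the outcome. The mean of the kept days then tends to exceed the true mean, and a treatment contrast is distorted if treatment changes how many hours pass. In the next-day path of H4, a sedentary following day may drop out because it was sedentary.

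**Working it through.** No figure in the plan depends on the valid-day rule, so there is none to reproduce. The check applies the rule directly and then illustrates the possible size.

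**1. One hour.** With n stepping minutes in 60, the shortest achievable longest zero-step run is (60 − n)/(n + 1), rounded up.
- n = 1: 59/2, rounded up = 30, so the hour fails.
- n = 2: 58/3, rounded up = 20, so the hour can pass.

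Two well-placed stepping minutes are enough. A day can therefore be kept on 10 × 2 = 20 stepping minutes, so the rule does not measure total activity either.

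**2. One fully worn day.** Let H be waking hours and F the waking hours holding a run over 20 minutes. Sleeping hours are assumed to have no steps, so they fail too. Valid hours = H − F, and the day is dropped when H − F < 10, that is when F ≥ H − 9.
- H = 16: dropped from F = 7, since 16 − 7 = 9.
- H = 14: dropped from F = 5. H = 18: dropped from F = 9.

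The value 16 is borrowed from the random prompts, sent in "four evenly spaced time windows: 0-4, 4-8, 8-12-, and 12-16-hours post-waking" and used only in the Formative Study. The rule itself sets no day length.

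| How the two sentences combine | Worn day, H = 16, F = 7 |
|---|---|
| Step clause alone | 9 valid hours, dropped |
| Heart rate and step clause both required | 9 valid hours, dropped |
| Heart rate alone | at least 16 valid hours, kept |

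**3. How often this could happen (illustration).** Let each minute be a stepping minute independently with probability q. The probability of no zero-step run over 20 in t minutes is A(t) = 1 for t ≤ 20, and otherwise the sum over j = 0 to 20 of (1 − q)^j · q · A(t − j − 1). Then p = A(60), and P(day kept) = P(Binomial(H, p) ≥ 10).

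| Stepping min per hour (60q) | p | Kept, H = 14 | Kept, H = 16 | Kept, H = 18 |
|---|---|---|---|---|
| 3 | 0.144 | 0.00 | 0.00 | 0.00 |
| 4.8 | 0.358 | 0.01 | 0.03 | 0.07 |
| 6 | 0.504 | 0.09 | 0.24 | 0.42 |
| 7.2 | 0.633 | 0.37 | 0.63 | 0.82 |
| 9 | 0.781 | 0.83 | 0.96 | 0.99 |
| 12 | 0.920 | 1.00 | 1.00 | 1.00 |

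With heart rate as the wear signal, every entry in the last three columns would be 1. Clustered stepping lowers retention: in a simulation with 2-minute stepping bouts and sitting bouts averaging 10 minutes (about 160 stepping minutes over 16 hours), about 33% of days are kept.

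**4. What it could do to a contrast (illustration).** Assumptions: 16 waking hours, 500 steps in a passing hour and 120 in a failing one, and an hourly pass probability that varies between days on the logit scale with SD 0.5 or 0.8. Over medians from 0.45 to 0.90, between 21% and 99% of worn days are kept, and the kept-day mean is 1.002 to 1.346 times the true mean (1.022 to 1.046 at a median of 0.80).
- *Single sessions.* The goal sessions are delivered "On days participants have planned to do physical activity (according to the Sunday scheduling survey"), so this case is the closest to the protocol. Adding 3,000 steps in one random waking hour, which then passes, on one day in seven gives an estimated effect of about 1.00 to 1.13 times the true one. The share of days kept differs between arms by under 3 percentage points, even at three days in seven.
- *All-day change.* If treatment raises the hourly pass probability by 0.09, the estimated effect at a median of 0.80 is 0.61 to 0.78 of the true one when the median is shifted, and 0.73 to 0.82 when 0.09 is added to each day's probability. At a median of 0.65 the figures are 0.36 to 0.43 and about 0.51. At 0.90 they are 0.90 to 0.98 either way.

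In the all-day case treatment acts only by turning failing hours into passing ones, so part of the attenuation is built in.

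**The case against.** The strongest reply is that the text is unclear rather than wrong. The zero-step run might only flag possible non-wear, with heart rate then deciding whether the watch was worn. That reading gives the heart-rate sentence a purpose and would keep the sedentary day. It appears nowhere in the documents, though, and requiring heart rate in addition to the step clause does not restore the day. If that is the practice, it needs to be written down.

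It is also fair that the single-session case shows little bias, that every rate in the illustrations is assumed, and that a sensitivity analysis of this rule could fit under the general missing-data language. Those points limit the size claimed. They do not justify filtering on the outcome when a direct wear signal is already recorded.

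Four stronger readings are tempting and are not supported:
- *All sedentary days are lost.* A day with ten passing hours is kept, and two stepping minutes can pass an hour.
- *The payment standard contradicts the rule.* Payment is for "wearing the Fitbit Versa smartwatch all day and night (≥ 23 h/day"), which is a compensation condition rather than an analysis definition. The two can coexist.
- *The intent-to-treat approach is breached.* Participants stay in their assigned groups. The issue is which of their days are analysed.
- *The primary result is compromised.* The affective outcomes come from check-ins and goal sessions and are not computed from steps.

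**Conclusion.** The point holds and should be fixed. As written, the rule that selects days for the physical activity analysis contains no heart-rate term and can remove a fully worn day because of how its steps are spread. That follows from the wording and step 2 alone, given a number of waking hours. A reader might infer that the activity results must be biased by a known amount or in a known direction. The documents do not support that, because they give no hourly pass rates. Under the stated assumptions the distortion is slight when about 90% of hours pass or when the effect comes from single sessions, and it can be substantial when many hours fail and treatment changes all-day stepping. The point concerns the secondary outcome of H1-H3 and the endpoint of H4.

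**What to change.** Define an hour as valid by the presence of heart-rate data, with a threshold the team sets. One example is heart rate present in at least 40 of 60 minutes, which mirrors the rule's own 20-minute allowance. Keep the 10-hour minimum for a day. State whether it counts waking hours only and, if so, how these are set, since the Sunday survey is where participants are "asked about their tentative sleep and physical activity schedule for that upcoming week" and may not match the day as lived.

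Use the zero-step clause only as a sensitivity analysis. State there that 20 minutes means a consecutive run, and how a run crossing the hour boundary counts. If it meant total zero-step minutes, the clause would be far stricter.

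Fix the definition before outcomes are examined by condition, apply it to all data collected so far, and report excluded days by condition and period under both definitions.

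The cost is a few sentences in the analysis plan and a change to the processing code. Heart rate is already recorded continuously, so no new data are needed. The downside is that some retained days may have an incomplete heart-rate signal.
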